8.8 Missing Data

Missing data will be investigated, and multiple imputations will be used to account for missingness. Multiple imputations will be performed under the assumption that missing data are missing at random (MAR). If the validity of the MAR assumption is questioned, possible departures from MAR will be investigated by sensitivity analyses.

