8.4 Determination of Sample Size and Accrual Rate

Based on earlier studies (48) and the IMMPACT recommendations(28), a 30% or higher decrease in pain score from baseline to the end of the follow-up period is a sign of clinically meaningful efficacy of the drug regimen within a patient. A randomized trial of pregabalin for the treatment of radiotherapy-related pain in head-and-neck cancer patients (33) observed an at least 30% decrease in 33% of placebo-treated patients. This study will use a single-stage design to evaluate the hypothesis that patients treated with buprenorphine will achieve at least a 30% decrease in pain with probability exceeding 33%. Formally, the following hypotheses will be evaluated at a one-sided 5% significance level:

$$H_0: p (\geq 30\% \text{ decrease}) = 0.33 \quad \text{versus} \quad H_a: p (\geq 30\% \text{ decrease}) > 0.33.$$

With 18 subjects, the study will have at least 80% power to reject the null hypothesis if the probability of achieving at least 30% decrease in pain with buprenorphine is, in fact, 63%. The hypothesized effect is consistent with the efficacy seen with other active treatments. Specifically,

buprenorphine will be considered an acceptable pain control medication if 10 or more subjects out of the 18 experience at least 30% pain reduction. We will enroll 20 subjects to allow for 10% drop-out rate.

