The primary analysis will compare the proportion of patients achieving a 30% drop in pain scores to the null-hypothesis value of 33% at a one-sided 5% significance level using a binomial test. The number of patients using analgesic and non-analgesic medications, as well as the occurrence of adverse events, will be tabulated and presented as counts with percentages. The average weekly pain scores, MDASI-HN, and the PROMIS® measures will be reported with descriptive statistics (mean, standard deviation, median, and range). Patient level summaries of the pain score and PRO outcomes will be created by computing area under the curve (AUC) of weekly averages. Scatterplots will be used to explore their relationship which will be quantified by Spearman's correlation coefficient. Further correlational analysis will be done by linear regression and linear fixed models.

8.7 Rationale for not Having a Stopping Rule: This is a supportive care pilot study to determine

the efficacy of transdermal buprenorphine and oral tramadol drug combination in alleviating radiation-induced mucositis pain in head and neck cancer patients. These pain medications are FDA approved and have an established safety profile. In addition to the primary efficacy endpoint, we will be evaluating other secondary end points, such as real-time pain monitoring through the OM Pain App. This will continue, even if the study drug regimen is discontinued for lack of efficacy or some other unspecified reason. This would provide us invaluable pilot data for future studies in this setting. Moreover, we have made provisions for switching to standard-of-care pain medications, such as oral oxycodone in our study for patients who don't derive adequate pain relief from the study regimen. Hence, it is reasonable to exclude a formal stopping rule for this trial.

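### Multiple imputation is not linked to the 10-of-18 responder rule, and that rule does not fit an efficacy population of up to 20

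*Combined protocol and SAP*

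**What the plan says.** - **Decision rule (Section 8.4).** "the following hypotheses will be evaluated at a one-sided 5% significance level", with a null rate of 33%. The rule is that buprenorphine "will be considered an acceptable pain control medication if 10 or more subjects out of the 18 experience at least 30% pain reduction". Twenty are enrolled to allow for 10% drop-out.
- **Test (Section 8.6).** The responder proportion is compared with 33% "at a one-sided 5% significance level using a binomial test". The same section makes at least two weeks on the regimen a condition for being evaluable.
- **Population (Section 8.3).** Efficacy is analysed in everyone who received at least one dose.
- **Missing data (Section 8.8).** "Multiple imputations will be performed under the assumption that missing data are missing at random (MAR". Departures from MAR are to be examined by sensitivity analyses, but only if MAR is called into question, and the method is not described. No imputation model, predictor list or pooling rule is given.
- **Follow-up after stopping (Sections 4.11, 5.2 and 8.7; study calendar note 2).** A patient who comes off the regimen stays in the study and pain data continue. Under Section 5.4, monitoring pauses during an admission that needs IV pain medication and then resumes.

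**The concern.** A binomial rule needs one whole-number count and one denominator. Imputation gives a separate count in each completed data set, and the plan has no step from those counts to a yes or no. The denominator is also unsettled: 18 in Section 8.4, all treated in Section 8.3, and those with two weeks of treatment in Section 8.6. With this sample size one responder decides the result, so an analyst could choose among defensible readings after seeing the data.

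The second issue is direction. Imputing from completers under MAR gives a missing patient roughly the completers' chance of response. If missing patients are mostly failures, the imputed count is too high and the false-positive rate rises.

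**Working it through.** **Inputs.** Section 8.4 gives p0 = 0.33, p1 = 0.63, one-sided 5%, n = 18, cut-off 10, 20 enrolled and 10% drop-out. Section 8.3 gives the treated set, taken as 20. The documents do not give the share of missing patients who are failures or the imputation model; both are varied below as assumptions.

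**1. The plan's own figure.** The error is P(X ≥ r | n, 0.33) and the power is P(X ≥ r | n, 0.63).
- n = 18, r = 10: error 0.0405, power 0.816. This agrees with "With 18 subjects, the study will have at least 80% power to reject the null hypothesis".
- n = 18, r = 9: error 0.102, so 10 is the right cut-off for 18.

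**2. The same cut-off with all treated patients.**
- n = 20, r = 10: error 0.087.
- n = 20, r = 11: error 0.035, power 0.835.

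**3. Imputation when missing patients tend to be failures.** The true rate over all N treated is held at 0.33. With k missing, a fraction f of them failures, the completers' rate is (0.33N − k(1 − f))/(N − k). For N = 20, k = 2, f = 1 it is 6.6/18 = 0.367. Each missing response is drawn from a Beta(x + 0.5, N − k − x + 0.5) posterior, where x is the number of observed responders. Earlier pain scores are ignored, and results are pooled by Rubin's rules with a one-sided z test. Simulated error at N = 20:

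| Failure share among missing | 2 missing | 4 missing |
|---|---|---|
| 67% (uninformative) | 0.041 | 0.046 |
| 80% | 0.054 | 0.084 |
| 90% | 0.067 | 0.119 |
| 100% | 0.081 | 0.170 |

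If the number of failure-only gaps varies around 10% instead of being exactly two, the N = 20 error is about 0.09 with Rubin pooling and 0.101 if the mean imputed count is rounded. With 18 analysed and two missing, both failures, it is 0.095 to 0.100.

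**4. Imputation that uses earlier scores.** Suppose earlier scores lead the model to give failures an imputed response chance of 10% to 20% (assumed). With 2 of 20 missing, both failures, the error is about 0.03 to 0.06.

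**5. No imputation.** Applying 10 of 18 to completers after two failure drop-outs gives P(X ≥ 10 | 18, 0.367) = 0.080.

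**6. Missing counted as non-response.** The analysed count can never exceed the true count, so the error is at most 0.035 (11 of 20) or 0.0405 (10 of 18), whatever the missingness. For power at n = 20:
- If 63% refers to all treated patients: P(X ≥ 11 | 20, 0.63) = 0.835.
- If 63% refers to completers and 10% are missing: the rate is 0.9 × 0.63 = 0.567, and P(X ≥ 11 | 20, 0.567) = 0.650.

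**The case against.** A reader might infer that patients who leave because of poor pain control or side effects will be missing at week 9. The documents do not support that. Section 5.2 lists these as reasons to come off the regimen and says data collection continues. Sections 4.11 and 8.7 agree, and study calendar note 6 allows questionnaires by telephone in weeks 8 to 12. The remaining routes are full or investigator withdrawal (4.11), loss to follow-up (4.12) and the admission pause (5.4). Only the last is tied to pain by design, and it is temporary. This objection stands and limits the expected amount of missing data.

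A reader might also infer that multiple imputation cannot be combined with a binomial test. That too goes beyond the evidence. With uninformative drop-out, pooled rules, including the median exact p-value, gave errors of about 0.04 to 0.06. What is missing is a stated rule.

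Section 8.8 does mention sensitivity analyses for departures from MAR, so the assumption is not ignored. And a binomial test run on 20 patients under Section 8.6 would itself require 11 responders; the 0.087 arises only if the written cut-off of 10 is carried over. Both points are fair. But the sensitivity analysis is conditional and undefined, and the only success criterion written down is 10 of 18.

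**Conclusion.** The concern holds as a specification gap in the primary analysis. The plan does not connect imputed data to the count rule, and the rule is calibrated for a different n from the efficacy population. If 10 is applied to 20 patients, the error is 0.087 against a stated 5%.

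The added risk from imputation depends on assumptions. At 10% missing the error ranges from about 0.04 to 0.10. The upper end, 0.09 to 0.10, requires that every missing patient is a failure and that the model ignores earlier scores. The documents state neither, and weekly BPI and daily app scores are collected and could serve as predictors. A reader might conclude that imputation under MAR doubles the error rate. That describes the worst case only, and the cause is informative missingness: a completers-only analysis without imputation gives 0.080 under the same drop-out. Removing imputation without a rule for missing patients would therefore not solve the problem.

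**What to change.** - **Denominator.** Name one primary analysis set and reconcile the all-treated population of Section 8.3 with the two-week evaluability condition of Section 8.6.
- **Missing week-9 response.** Count it as non-response in the primary analysis.
- **Test.** Run one exact binomial test on the observed count, with the cut-off tied to the actual n. For 20 treated patients it is 11 (error 0.035, power 0.835 if 63% refers to all treated).
- **Imputation.** Keep it as a prespecified sensitivity analysis that is always reported. State the model, with weekly BPI and app scores as predictors, and the pooling rule.
- **Power.** Restate it and say whether 63% refers to all treated patients or to completers.

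These are wording changes; the number enrolled and the data collected stay the same. The cost is conservatism. With 10% missing and 63% among completers only, power is about 65%. If missingness is unrelated to outcome, the error also falls well below 5%: about 0.014 in simulation with 10% of 20 missing.

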8.9 Research Environment

The study will be activated at the Medical College of Wisconsin (MCW) Cancer Center. The cancer center employs 57 full-time and two part-time staff. It is the only academic cancer center in Eastern Wisconsin, supporting more than 2.3 million people. The MCW Cancer Center Clinical Trials Office (CTO) will conduct the study and support all stages of the clinical trial process, including: protocol feasibility, regulatory support, compliance monitoring, consent development, IRB submission, budget development, contract negotiation, trial coordination and management, trial promotion and referrals, and patient screening, enrollment and consenting, data collection and management and results monitoring and reporting. The Division of Biostatistics at MCW will provide statistical support and perform analysis. As a recipient of a clinical and translational science award from NIH, with a recent five-year, \$20 million renewal, the Medical College of Wisconsin is representing a consortium of Milwaukee institutions (Clinical and Translational Science Institute of Southeast Wisconsin [CTSI]) working in collaboration to advance biomedical research, clinical care, and education.

9 DATA AND SAFETY MONITORING PLAN (DSMP)

9.1 Data and Safety Management Overview

The Medical College of Wisconsin (MCW) Data Safety Monitoring Committee (DSMC) and the MCW Institutional Review Board (IRB) will approve protocol-specific DSM plans. A local, investigator-initiated trial will be required to be continuously monitored by the principal investigator of the study with safety and progress reports submitted to the DSMC.

9.2 Study Team

The study team minimally consists of the principal investigator, the clinical research coordinator, regulatory specialist, and the study biostatistician. While subjects are on study, the principal investigator will meet regularly with the research coordinator and the study biostatistician to review study status. This review will include but not be limited to reportable SAEs and UPIRSOs and an update of the ongoing study summary that describes study progress in terms of the study schema.

The appropriateness of further subject enrollment and the specific intervention for the next subject enrollment is addressed. All meetings including attendance are documented.

9.3 Quality Assurance

The MCWCC Clinical Trials Office provides ongoing quality assurance audits. This protocol was classified as intermediate risk and will be reviewed internally by the MCW Cancer Center Clinical Trials Office Quality Assurance Staff according to the MCW Cancer Center Data and Safety Monitoring Plan and current version SOP, 6.5.2 Internal Quality Assurance Reviews.

9.4 Clinical Trials Office

The MCWCC Clinical Trials Office [CTO] provides administrative assistance and support to the DSMC.

9.5 DSMC

The Medical College of Wisconsin Cancer Center places the highest priority on ensuring the safety of patients participating in clinical trials. Every cancer interventional trial conducted at MCW includes a plan for safety and data monitoring.

More information can be found related to the MCWCC Data and Safety Monitoring Plan at the MCWCC website ([Data and Safety Monitoring Plan](#)).

This study will be reviewed by the Medical College of Wisconsin Cancer Center Data and Safety Monitoring Committee (MCWCC DSMC). A summary of the MCWCC DSMC activities are as follows:

- Review the clinical trial for data integrity and safety.
- Review all DSM reports.
- Submit a summary of any recommendations related to study conduct.
- Terminate the study if deemed unsafe for patients.

A copy of the MCWCC Data and Safety Monitoring Plan and membership roster will be maintained in the study research file and updated as membership changes. The committee will review reports from the study PI twice annually (or more frequently if needed) and provide recommendations on trial continuation, suspension, or termination as necessary.

Any available DSMC letters will be submitted to the IRB of record as required.

10 REGULATORY COMPLIANCE, ETHICS, AND STUDY MANAGEMENT

This study will be conducted in accordance with the ethical principles that have their origin in the Declaration of Helsinki as stated in 21 CFR §312.120(c)(4); consistent with GCP and all applicable regulatory requirements.

10.1 Regulatory Compliance

This study will be conducted in compliance with:

- The protocol.
- Federal regulations, as applicable, including 21 CFR 50 (Protection of Human Subjects/Informed Consent); 21 CFR 56 (Institutional Review Boards) and 45 CFR 46 Subparts A (Common Rule), B (Pregnant Women, Human Fetuses and Neonates), C (Prisoners), and D (Children), GCP/ICH guidelines, and all applicable regulatory requirements. The IRB must comply with the regulations in 21 CFR §56 and applicable regulatory requirements.

10.2 Prestudy Documentation

Prior to implementing this protocol at MCWCC, the protocol, informed consent form, HIPAA authorization and any other information pertaining to participants must be approved by the MCW IRB. 10.3 Institutional Review Board

The protocol, the proposed informed consent form, and all forms of participant information related to the study (e.g., advertisements used to recruit participants) will be reviewed and approved by the MCW Institutional Review Board. Before obtaining MCW approval, the protocol must be approved by the Medical College of Wisconsin Cancer Center Scientific Review Committee. The initial protocol and all protocol amendments must be approved by the IRB before implementation.

Informed Consent Process

Informed consent is a process that is initiated prior to the individuals agreeing to participate in the study and continues throughout the individual's study participation. Extensive discussion of risks and possible benefits of this therapy will be provided to the subjects and their families. Consent forms describing in detail the study interventions/products, study procedures, and risks are given to the subject and written documentation of informed consent is required prior to starting intervention/administering study product.

Consent forms will be IRB approved and the subject (and legally authorized representative, if necessary) will be asked to read and review the document. Upon reviewing the document, the investigator will explain the research study to the subject and answer any questions that may arise. In accordance with 46 CR 46.111, the subject will sign and date the informed consent document prior to any procedures being done specifically for the study.

A witness should only sign when required, per FH/MCW IRB policy. If a witness signs the document when not required, the study staff should document in the legal medical record (or note to file) the relationship to the patient and why a witness signed. (i.e., "Although not required, the subject's spouse was present during the consenting process and signed as the witness." Or "Although not required, the hospital staff was present for the consenting process and signed as a witness.")

The subjects will have the opportunity to discuss the study with their surrogates or think about it prior to agreeing to participate. The subjects may withdraw consent at any time throughout the course of the trial.

A copy of the informed consent document will be given to the subjects for their records. The rights and welfare of the subjects will be protected by emphasizing to them that the quality of their medical care will not be adversely affected if they decline to participate in this study. If there are changes to the consent form, all revisions will be reviewed with the study subject at the next appropriate opportunity. Patients who require reconsenting will be defined in the IRB-approved amendment submission. The process for obtaining informed consent will again be performed. Study subjects will not be reconsented for continuing reviews. The MCWCC CTO will follow the MCW/FH IRB's policy for subjects who demonstrate limited English proficiency or limited literacy.

After the subject's visit in which the consent is signed, it is documented in the clinic chart that the consent has been signed and that all questions have been answered to the subject's satisfaction after adequate time for the review of the consent. It is also documented that a copy of the consent is given to the subject. The original consent is kept with the subject's study file, and a copy of the consent is sent to the OCRICC office, which will then submit to HIM a copy of the signed consent to be scanned into EPIC, the legal medical record.

10.4 Subject Confidentiality and Access to Source Documents/Data

Subject confidentiality is strictly held in trust by the sponsor-investigator, participating investigators, and any staff, [and the sponsor(s) and their agents] (include bracketed portion if applicable). This confidentiality includes clinical information relating to participating subjects, as well as any genetic or biological testing.

The study protocol, documentation, data, and all other information generated will be held in strict confidence. No information concerning the study, or the data will be released to any unauthorized third party without prior written approval of the principal investigator.

The conditions for maintaining the confidentiality of the subjects' records are required for the life of the data. These rules apply equally to any and all MCWCC projects.

One risk of taking part in a research study is that more people will handle the personal health information collected for this study. The study team will make every effort to protect the information and keep it confidential, but it is possible that an unauthorized person might see it. Depending on the kind of information being collected, it might be used in a way that could embarrass the subject or affect his/her ability to get insurance.

While data are being collected and after all data have been collected but are still in the process of being analyzed, the subject's data/PHI are stored in the locked clinical research office in the Clinical Trials Office. Databases in which the study subject information is stored and accessed are password protected, allowing for limited access by authorized personnel only. Data/PHI kept in the case report forms contain the study identifiers, subject initials, date of birth, and date of service.

The principal investigator will allow access to all source data and documents for the purposes of monitoring, audits, IRB review, and regulatory inspections.

The study monitor/s or other authorized representatives of the principal investigator may inspect all documents and records required to be maintained by the investigator, including but not limited to, medical records (office, clinic, or hospital) and pharmacy records for the subjects in this study. The clinical study site will permit access to such records.

10.5 Protection of Human Subjects

10.5.1 Protection from Unnecessary Harm

Each clinical site is responsible for protecting all subjects involved in human experimentation. This is accomplished through the IRB mechanism and the informed consent process. The IRB reviews all proposed studies involving human experimentation and ensures that the subject's rights and welfare are protected and that the potential benefits and/or the importance of the knowledge to be gained outweigh the risks to the individual. The IRB also reviews the informed consent document associated with each study to ensure that the consent document accurately and communicates the nature of the research to be done and its associated risks and benefits.

10.5.2 Protection of Privacy

As noted, patients will be informed of the extent to which their confidential health information generated from this study may be used for research purposes. Following this discussion, they will be asked to sign informed consent documents. The original signed document will become part of the patient's medical records, and each patient will receive a copy of the signed document.

10.5.3 Changes in the Protocol

Once the protocol has been approved by the MCW IRB, any changes to the protocol must be documented in the form of an amendment. The amendment must be signed by the investigator and approved by IRB prior to implementation.

If it becomes necessary to alter the protocol to eliminate an immediate hazard to patients, an amendment may be implemented prior to IRB approval. In this circumstance, however, the investigator must then notify the IRB in writing within five working days after implementation.

The IRB may provide, if applicable regulatory authority(ies) permit, expedited review, and approval/favorable opinion for minor change(s) in ongoing studies that have the approval /favorable opinion of the IRB. The investigator will submit all protocol modifications to the sponsor and the regulatory authority(ies) in accordance with the governing regulations.

Changes to the protocol may require approval from the sponsor.

Any departures from the protocol must be fully documented in the source documents.

